##### **Phase 2 observational study.**

When Phase 2 is activated, it will be implemented at each participating site when all required approvals are in place. Phase 2 consists of the development of a prospective observational study which will collect the same data as for the Phase 1 registry, as well as additional data such as dates of events and date of birth which are considered pseudonymised data. For this reason, informed consent/assent will be required from participants and/or their legal guardian. Patients (and/or their legal guardian) may be asked for permission to link their data to other medical records, and to be contacted for further research studies.

If the patient/legal representative does not give consent to participate in Phase 2, the study team will proceed with entering data only into the Phase 1 anonymous registry database.

The eCRF will be based on routine patient visits, and all visits from initial presentation (diagnosis or admission) onwards (follow-up visits) will be entered, until the infant, child or adolescent is considered fully discharged from care (outcome visit). Follow-up of infants born to adolescent mothers who acquired mpox in pregnancy to ascertain neonatal outcomes should end at or before day 28 after the baby is born. If consent is sought for collecting detailed information on infants who acquired mpox and whose mothers are already recruited in the study, linkage of maternal study ID and infant study ID will be made (see section 6.1 for more details).

Only routinely collected clinical data will be entered in the database.

## 3.2 STUDY TIMELINES

The study will aim to collect all data over approximately 18 months.

Study activity*	Project Month (calendar month) **
M24 Paediatric registry online (Phase 1 start)	12 (Oct 2023)
Del 7.15 Study initiation package	16 (Feb 2023)
Database Phase 2 go live (Phase 2 start)	The decision about whether to carry phase 2 will be based on an assessment of ongoing case numbers and the existence of other surveillance systems/studies.
Interim analysis	22 (Aug 2023)
Del 7.16 Midterm recruitment report	24 (Ott 2023)
Final analysis	45 (July 2025)
D 7.18 Report on status of posting results (Final report)	48 (Oct 2025)

\* Month numbers measured from start of VERDI project (November 2021).

\*\*VERDI project timelines are reported in *italics*.

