##### **Phase 1 registry.**

An online registry will be developed to collect anonymised routine clinical data on patients with laboratory confirmed mpox infection aged <18 years. This may include pregnancy and neonatal data both for adolescents who are pregnant or up to 28 days postnatal and have mpox, and infants diagnosed with mpox in the neonatal period. Because all data collected will be fully anonymised, ethics approval may not be required in some or all countries, allowing swift implementation of the registry in response to an outbreak.

Data to be collected include clinical characteristics, symptoms and disease severity, treatments received and outcomes. Data for each patient will be reported at a single point in time, at the end of the clinical episode (e.g. at discharge from care). Data will be collected on historic cases (occurring before the inception of the registry), and on incident cases where relevant approvals and/or consent have not been obtained for Phase 2. Only routinely collected clinical data will be reported.

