### **7.2 SAMPLE SIZE**

In Phase 1, the preliminary analysis will be largely descriptive. Therefore, no formal sample size calculation has been undertaken, and instead all available data on cases will be utilised. Future specific analyses in Phases 1 and 2 will be assessed for feasibility based on the numbers of cases reported and their characteristics (e.g. numbers with and without a particular exposure of interest, such as age or vaccination).

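### Does the misprinted Phase 1 start date, set against the 18-month collection period, make the study timeline unworkable?

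*Protocol*

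**What the plan says.** Section 3.2 (Study Timelines) opens with "The study will aim to collect all data over approximately 18 months". The table beneath gives a project month and a calendar month for each milestone:

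| Milestone | Project month | Printed date |
|---|---|---|
| Registry online (Phase 1 start) | 12 | October 2023 |
| Study initiation package | 16 | February 2023 |
| Interim analysis | 22 | August 2023 |
| Midterm recruitment report | 24 | October 2023 |
| Final analysis | 45 | July 2025 |
| Final report | 48 | October 2025 |

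The footnote fixes the origin: "Month numbers measured from start of VERDI project (November 2021". Phase 2 has no date; its row says "The decision about whether to carry phase 2 will be based on an assessment of ongoing case numbers" and on what other surveillance systems or studies exist.

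Two other places bear on the point. Section 3.1, under the Phase 1 registry, says "Data will be collected on historic cases (occurring before the inception of the registry", as well as on incident cases not covered by Phase 2. Section 7.2 says that "no formal sample size calculation has been undertaken" and that every available case will be used.

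**The concern.** The registry appears to open after its own interim analysis, and the midterm recruitment report appears to fall in its opening month. Taking the project month as right and the printed year as wrong cures that, but collection then seems to stop well over a year before the final analysis. Taking October 2023 as right fits the final analysis but not the interim.

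If these dates governed the data, the stakes would be real. An interim analysis could have nothing to analyse. The line between historic and incident cases could move by 12 months. Cases arising late in the period could be left out of a final analysis that is meant to describe how cases are distributed over time.

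**Working it through.** **Inputs.** All dates, the November 2021 origin and the 18-month period come from section 3.2.

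**Step 1: reproduce the table.** Calendar month = November 2021 + (project month − 1).

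- Month 12: October 2022. Printed October 2023; does not agree.
- Month 16: February 2023. Agrees.
- Month 22: August 2023. Agrees.
- Month 24: October 2023. Agrees.
- Month 45: July 2025. Agrees.
- Month 48: October 2025. Agrees.

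Treating November 2021 as month 0 moves every date one month later and matches no row. The convention is therefore clear, and one cell is out by 12 months.

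**Step 2: test the sequence under each possible start.** Collection end = start + 18 months. The gap is July 2025 minus that end. The third row is an assumption, since the protocol does not say when the 18 months begin.

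| 18 months counted from | Interim (August 2023) relative to this start | Collection ends | Gap to final analysis |
|---|---|---|---|
| October 2022 (month 12) | +10 months | April 2024 | 15 months |
| October 2023 (as printed) | −2 months | April 2025 | 3 months |
| February 2023 (initiation package) | +6 months | August 2024 | 11 months |

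Only the printed October 2023 start gives an impossible order. From October 2022 the interim comes at +10 months, the midterm report at +12, the end of collection at +18 and the final analysis at +33. That order is workable. The 15 months after collection are 15/33 = 45% of the span from opening to final analysis: long and unexplained, but not inconsistent with a period worded as an approximate aim.

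**Step 3: see what depends on these dates.**

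- *Inclusion.* Section 4.1 sets age at diagnosis and laboratory confirmation, with no calendar limit. Section 7.2 takes all available cases. No section says that opening plus 18 months selects the final analysis set.
- *Historic or incident.* Section 3.1 ties this to the registry's inception, and section 5 to activation of data entry. Both are events, so the actual opening sets the boundary whatever the table prints. In Phase 1 both kinds of case go into the same anonymised database as one end-of-episode report, and section 7.3 lists no analysis by this split. Whether an incident case goes to Phase 1 or Phase 2 depends on Phase 2 approvals and consent, not on the Phase 1 opening date.
- *Interim analysis.* Section 7 attaches no test, stopping rule or error rate to it. Section 3.2 bases the Phase 2 decision on case numbers and other surveillance, without reference to the interim.
- *Precision.* There is no sample size target for a shorter or longer window to miss.

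**The case for a change.** The strongest case for a change is that the reader cannot tell which half of the cell is wrong. The month number and the interim date favour October 2022. Against that, an 18-month period fits the July 2025 final analysis better from October 2023. The reference list also includes a source accessed on 5 December 2022, while section 3.1 still speaks of the registry as yet to be developed, so the text was written after October 2022 but treats the opening as future. In addition, the protocol gives no data cut-off, so the 18 months are its only indication of when collection ends. A site might not know whether to enter a case from late 2024, and temporal distribution is a listed Phase 1 objective.

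Much of this is fair. The cell is wrong, the document does not settle how, and the starting point of the 18 months is unstated. What does not stand is the step to a consequence for results. Because historic cases are entered as well, a wrong opening date excludes nobody. Only a firm closing date could exclude cases, and the protocol sets none: it states an approximate aim for the study as a whole, including a Phase 2 that may come later and fill part of the interval. A cut-off for a given analysis is commonly fixed in the analysis plan, which is not at hand. Extending collection to just before July 2025 would be a preference about duration, not the correction of an error.

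**Conclusion.** No change to the plan follows. There is one clerical slip: the Phase 1 start row is 12 months out of step with its own project month and, as printed, puts the opening 2 months after the interim analysis. The study team would meet this as soon as it scheduled the interim, and would move the date or correct the cell without touching any method.

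The gap before the final analysis is 15 months if the 18 months run from October 2022, 11 if from February 2023 and 3 if from October 2023. It rests on a starting point that the protocol does not state and on no later Phase 2 collection. It is a gap in a planning table, not a contradiction.

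The conclusion rests on three features of the protocol: the study is primarily descriptive with no formal sample size, inclusion and the historic/incident split do not depend on the printed date, and no decision is tied to the interim. Reconciling the start row with its month number and the interim and midterm rows, and saying when the 18 months begin, is worthwhile housekeeping at the next revision. It would alter no estimate or conclusion.

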## 4 ELIGIBILITY CRITERIA

All patients with laboratory-confirmed mpox infection seen in hospitals as well as primary/community care settings will be eligible for inclusion in Phases 1 and 2.

### 4.1 INCLUSION CRITERIA

For the Phase 1 registry all infants, children and adolescents aged <18 years at the time of mpox diagnosis, with laboratory-confirmed mpox infection, as per national guidelines, will be eligible for inclusion in the anonymised dataset. Moreover, mothers of eligible infants who are diagnosed with mpox at 28days or less are included in the study to collect maternal data on pregnancy and delivery..

For the Phase 2 observational study all patients meeting the inclusion criteria for Phase 1 will be eligible for inclusion. Patients and their legal guardians will be required to give informed consent/ assent.

## 5 STUDY PROCEDURES AND SITES

For Phases 1 and 2, there will be no change to patient care as a result of inclusion in the study; data will be collected on clinical status, treatments received, and outcomes as recorded in routine care and not according to a defined schedule of procedures.

**Phase 1** will collect basic, routine and anonymised data. Where required, each site will be responsible for seeking the country-appropriate ethics approvals or waivers, and it is expected that most will be granted waivers or provide evidence that approval is not required. The link to the online data capture system will be shared through existing networks of clinicians and researchers working in related areas, with an invitation to enter details on all cases of mpox infection aged <18 years seen in their centres. This will include retrospective entry of cases seen before activation of the data entry system as well as incident cases, where approvals are not yet in place for Phase 2, or participants have not consented to Phase 2. Summary data will be entered at the end of each patient's clinical episode.

Patients already entered into the Phase 1 database will not be contacted to give their consent to join Phase 2, to avoid duplication.

For **Phase 2**, patients and (where appropriate) their legal guardians will be informed about the study and asked for consent / assent to take part (see further details in Section 8.3: Informed Consent). Consent can be sought at any point from first presentation (at diagnosis or admission) of the patient until discharge from care. Where consent is given, the 'Initial Presentation Form' in REDCap should be completed as soon as possible and thereafter, each site can decide to perform the data entry following each patient visit or at the point of patient discharge from care. Longer term follow-up or enhanced data collection may be enabled through linkage to routine data sources (e.g. hospital and primary care records), if additional consent is granted.

Where consent is not given for Phase 2, anonymised data will be entered as in Phase 1 (if permitted under local ethics requirements).

Specific study procedure relevant to **Phase 3** will be detailed in the appropriate sub study protocol.

### 5.1 STUDY SITES

Phase 1 of the study will be cascaded through VERDI, Penta and VACCELERATE networks (in endemic and non-endemic countries). Additionally, Phase 1 will be advertised to other national and international networks, in order to increase the representation of further countries. Sites will be provided with log-in details enabling entry of anonymous information into the REDCap server following confirmation by the Sponsor of receipt of appropriate approvals, waivers, or evidence confirming that approvals are not required.

For Phase 2 the Sponsor will be conducting site feasibility assessments and selection according to presence of cases, willingness to be involved and appropriate resources at site level to gain approvals and enter data. The Sponsor will provide sites with the study documents (inclusive of Patient Information Sheet, Consent forms, privacy notice and CRF forms) for ethics submissions.

## 6 DATA MANAGEMENT

### 6.1 REDCAP

Source documents are represented by documents where data are first recorded, and from which participants' electronic case report forms (eCRF) data are obtained. These include, but are not limited to, hospital records (from which medical history and previous and concurrent medication may be summarised into the CRF).

In this study, primary data sources are collected in eCRFs completed by study staff at participating sites. Source data will be collected directly into a web-based REDCap database specifically designed by the study team. A separate but interoperable REDCap database will be developed for each phase: 1) the unconsented, anonymised data, 2) consented, pseudonymised data, and 3) each additional sub study initiated in Phase 3 (each to be described in its own protocol).

To enhance accuracy, data will be subjected to logic and consistency checks, e.g., for implausible values and inconsistencies. Potential errors will be investigated and discussed between the data manager, statisticians, and individual sites.

In Phase 1, data for each patient will be entered at the end of clinical follow-up and each clinical site will transcribe into the eCRF only anonymous retrospective data from source data. No personal identifiable data will be entered into the eCRF (e.g., date of birth will be replaced with age group at diagnosis).

[figure not shown]
In Phase 2, pseudonymised data will be collected. The 'Initial Presentation Form' in REDCap should be completed as soon as possible and thereafter, each site can decide to perform the data entry following each patient visit or as in Phase 1, at the point of patient discharge from care.

In Phase 1 data will be fully anonymous therefore no identifiers will be recorded, whereas in Phase 2 the participants will be identified by a unique study-specific number and/or code in any database. The name and any other identifying detail will be retained only by the site staff on the consent form and the clinical records.

Phase 2 maternal-infant record linkage: If consent is sought for collecting detailed information on an infant with mpox whose adolescent mother has mpox and is already recruited in the study, the mother's study ID should be reported by the study staff on the newly generated infant record, to allow for linkage of maternal study ID and infant study ID.

Data may be shared with third parties subject to appropriate Data Sharing Agreements, with requests for access to data reviewed in accordance with the VERDI Data Management Plan (see further details in Section 10).

The diagram below illustrates the data flow for the study.

\*Unconsented data will be fully anonymised;  
consented data will be pseudonymised

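### Phase 1 does not say which centre reports a child managed at more than one, so a child may be entered twice with no stated means of confirming it

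*Protocol*

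**What the plan says.** **Who enters.** Section 5 circulates the data-capture link through clinical and research networks, "with an invitation to enter details on all cases of mpox infection aged <18 years seen in their centres". Past and incident cases both qualify. Under section 4, patients "seen in hospitals as well as primary/community care settings will be eligible for inclusion in Phases 1 and 2". Section 5.1 spreads Phase 1 through three named networks and advertises it to others.

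**When.** Section 3.1 (Phase 1 registry) asks for each patient's data once, when the clinical episode ends, and gives discharge from care as an example.

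**What is stored.** Section 6.1: "In Phase 1 data will be fully anonymous therefore no identifiers will be recorded", and "date of birth will be replaced with age group at diagnosis". Section 3.1 lists as extra to Phase 2 the "additional data such as dates of events and date of birth which are considered pseudonymised data".

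**Protection against duplicates.** The only stated rule is in section 5: "Patients already entered into the Phase 1 database will not be contacted to give their consent to join Phase 2, to avoid duplication". Section 6.1 plans checks for implausible and inconsistent values, with queries to sites. It names no duplicate check.

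**Mothers and infants.** On Phase 1 content, section 3.1 says: "This may include pregnancy and neonatal data both for adolescents who are pregnant or up to 28 days postnatal and have mpox". It then adds infants diagnosed in the neonatal period. Section 6.1 describes linkage of maternal and infant study IDs for Phase 2 only.

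**The concern.** The entry rule is written by centre, whereas the outputs are meant to be per child. A child referred from primary care to hospital, or moved between hospitals, meets the entry rule at each participating centre. Because the records are anonymous, the second centre cannot look up whether the child is already in the registry.

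The outputs at stake are those Phase 1 exists to produce. Section 7.3 lists the temporal and geographical distribution of cases, the proportions hospitalised and admitted to ICU, and the number of congenital infections. Section 1 notes that paediatric numbers have been small, so a few duplicates could move these figures. Any logistic regression under section 7.3 would also treat two records of one child as two independent children.

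This is not a detail to leave to an analysis plan. Which centre reports, and which items are collected, must be settled before data are entered.

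**Working it through.** The protocol gives no duplicate rate and no sample size, so there is no planned figure to reproduce. The check is first a reading of the text, then an illustration on assumed inputs.

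**Step 1: follow one child through the rules.** A child is seen at primary care centre A and referred to hospital B. Both participate.
- Section 5 invites A and B alike to enter the child, since each has seen the case.
- The timing rule in section 3.1 tells each to wait until the episode ends. It does not say whose discharge counts. A can regard the child as discharged from its own care, as can B later.
- The Phase 1 to Phase 2 rule is not triggered, because both entries are in Phase 1.
- The section 6.1 checks need not be triggered, because each record can be plausible and internally consistent.
- The analyst holds age group and clinical features, but no identifier or date of birth, and event dates are described as Phase 2 data. Section 6.2 describes an identification key for pseudonymised data only.

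Two centres can thus each follow the protocol and enter the same child, and no stated step would confirm it.

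**Step 2: hospitalised share (all inputs assumed).** Take 100 true cases, 20 of them hospitalised. Let d be the share of hospitalised children also entered by a referring centre.
- Both records note the admission: (20 + 20d) / (100 + 20d).
- Only the receiving centre's record notes it: 20 / (100 + 20d).

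| d | Records | Both note admission | Only one notes it |
|---|---|---|---|
| 10% | 102 | 22/102 = 21.6% | 20/102 = 19.6% |
| 25% | 105 | 25/105 = 23.8% | 20/105 = 19.0% |
| 50% | 110 | 30/110 = 27.3% | 20/110 = 18.2% |

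The true value is 20%. The case count is 2%, 5% or 10% too high. The bias in the share can go either way.

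**Step 3: ICU share (all inputs assumed).** Let the true share be p = 5%, with duplicate rates ds in ICU cases and dn in the others, and every duplicate carrying the same outcome. Observed share = p(1 + ds) / [p(1 + ds) + (1 − p)(1 + dn)].
- ds = 20%, dn = 2%: 0.060 / (0.060 + 0.969) = 5.8%; count 2.9% too high.
- ds = 40%, dn = 2%: 0.070 / (0.070 + 0.969) = 6.7%; count 3.9% too high.
- ds = 50%, dn = 0: 0.075 / (0.075 + 0.950) = 7.3%; count 2.5% too high.
- ds = dn = 10%: the share stays at 5.0% and the count is 10% too high. The true variance of the share is (1 + 3 × 0.10) / (1 + 0.10) = 1.18 times the naive one.

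**Step 4: congenital infections.** If infants were counted from both maternal and infant records, one infant counted twice among 5, 10 or 20 would inflate the number by 20%, 10% or 5%. The protocol does not say that they would be counted in this way.

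**The case against.** **One report per patient is already required.** Section 3.1 asks for a single report at the end of the episode. Read plainly, a child transferred in mid-illness has not reached that point at the referring centre, so the text leans towards the centre where care ends. This has weight, and it is why double entry is a possibility and not a certainty. It is still a rule about time: it names no centre. Entry is also by invitation, and a duplicate needs both centres to be participating.

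**Duplicates could be found.** A reader might infer that they are undetectable. The documents do not support that. Phase 1 records age group, sex, place, symptoms, lesion counts, treatments and outcomes. Entries are auditable under individual log-ins (section 6.3), and errors are discussed with sites, which hold the source records. With few cases, a likely pair could be noticed and queried. What stands is that no such screen is planned and no means of confirmation is stated.

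**Neonates.** A reader might also infer that an infected newborn of an infected adolescent is counted twice. That goes too far. No separate maternal form is described, neonatal fields on a mother's record do not add a case, and the result depends on how infants are counted. The firm point is only that linkage is stated for Phase 2 and not for Phase 1.

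**Unseen material.** The eCRF and the data-flow figure are not shown, and a Data Management Plan is referred to. A transfer item may already exist. The protocol would still lack a rule on which centre reports.

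**Anonymity is deliberate.** It is the stated price of rapid start-up, and the analysis is mainly descriptive. This is accepted, and the fix keeps full anonymity.

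**Conclusion.** The concern holds as a gap in the reporting rule. A child managed at two participating centres may be entered twice in Phase 1, and the protocol states neither which centre should report nor how a suspected duplicate would be confirmed. Case counts and the hospitalised and ICU proportions may be distorted.

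The size is unknown. The case numbers, the 20% and 5% shares and the duplicate rates used above are all assumptions. So is any view that sicker children are transferred more often. A reader might infer that severity is overstated, but the hospitalised share moves up or down according to what the referring centre records, and equal duplication leaves a share unchanged. No direction of bias can be claimed. This is a cheap improvement, best made before further data are entered, and not a flaw that undermines the registry.

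**What to change.** 1. In section 5, state that the centre where the episode of care ends enters the Phase 1 record. A referring centre enters it only if the receiving centre is not participating or its participation is unknown.
2. Add one anonymous eCRF item: patient transferred to or from another centre, where a record may also have been entered (yes / no / unknown).
3. Screen flagged records for likely duplicates together with the sites. Repeat the main proportions leaving out only the referring-centre record of each suspected pair. Leaving out all transferred children would discard validly entered cases.
4. Count congenital infections from infant records only, and add a yes/no item on whether the patient's mother or infant also has a Phase 1 record.

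Cost: a short addition to section 5, one or two extra items for sites to answer, and a small screening task. Anonymity and patient care are unchanged. The downside is that a few referred cases may be missed where the receiving centre does not report.
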